**Table 1 Schedule of Activities (SoA)**

|              | Screening                   |               | Treatment Period |             |                |             |                |             |                | EDV | Safety Follow-up period   | Final Follow-up Visit | Details in CSP Section or Appendix |
|--------------|-----------------------------|---------------|------------------|-------------|----------------|-------------|----------------|-------------|----------------|-----|---|-----------------------|------------------------------------|
|              | 1                           | 2             | 3                | 4           | 5 a | 6           | 7 a | 8           | 9 a |     |   |                       |                                    |
| Visit Number |                             |               |                  |             |                |             |                |             |                |     | 10, 11 a ,
12, 13 a ,
14, 15 a | 16                    |                                    |
| Study Week   |                             |               | 0                | 1           | 3              | 4           | 6              | 8           | 10             |     | 12, 14,
16, 18,
20, 22  | 24                    |                                    |
| Study Day    | D-42 to
D-1  | D-7 to
D-1 | D1               | D8          | D22            | D29         | D43            | D57         | D71            |     | D85,
D99,
D113,
D127,
D141,
D155                       | D169                  |                                    |
| Visit Window |                             |               |                  | ± 1
days | ± 2
days    | ± 2
days | ± 2
days    | ± 2
days | ± 2
days    |     | ± 2
days   | ± 2
days           |                                    |

Note: Participants are required to fast for at least 8 hours overnight prior to all study visits except for Visit 1; Participants are permitted to drink water during this period of fasting until 1 hour before blood sampling. On days where participants attend the clinic in a fasted state, blood and urine samples should be obtained prior to administration of IP.

Note: Samples to be obtained from all treatment arms unless specified in the table.

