### 3. OBJECTIVES AND ENDPOINTS

**Table 3 Objectives and Endpoints**

| Objectives   | Endpoints  |
|--|--|
| Primary   |  |
| 
 
To assess the effect of different doses of AZD8233 on LDL-C versus placebo
 
 | 
 
Absolute change from baseline in log-transformed LDL-C in plasma
 
   |
| Secondary   |  |
| 
 
To assess the effect of different doses of AZD8233 on PCSK9 versus placebo
 
 | 
 
Absolute change from baseline in log-transformed PCSK9 in plasma
 
   |
| 
 
To assess the effect of different doses of AZD8233 on LDL-C versus placebo
 
 | 
 
Percentage change from baseline in levels of LDL-C in plasma
 
   |
| 
 
To assess the effect of AZD8233 on other lipid parameters versus placebo
 
   | 
 
Levels of other lipid parameters including:               
 
- TC
 
- HDL-C
 
- Non-HDL-C
 
- VLDL-C
 
- ApoA1
 
- ApoB
 
- Lp(a)
 
- Triglycerides
 
- Remnants cholesterol
 
 
 
 |
| 
 
To evaluate the PK of AZD8233
 
  | 
 
Plasma parameters: population PK parameters to be reported in a separate report.
 
   |
| 
 
To evaluate the immunogenicity of AZD8233
 
                                  | 
 
Development of ADA and titer (if participants are ADA-positive) during treatment and follow-up
 
   |
| Safety  |  |
| 
 
To assess the safety and tolerability of AZD8233
 
                           | 
 
Safety and tolerability will be evaluated in terms of AEs, vital signs, ECG, and
 
   |

| Objectives  | Endpoints   |
|---|---|
|   | clinical laboratory evaluations including platelet count  |
| Tertiary/Exploratory  |   |

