The laboratory vendor personnel performing the bioanalyses of the plasma samples will have access to the randomization list.

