### **8.5.1 Pharmacokinetics**

Plasma samples will be collected for measurement of plasma concentrations of AZD8233 as specified in the SoA.

Samples may be collected at additional time points during the study if warranted and agreed upon between the Investigator and the sponsor, eg, for safety reasons. The timing of sampling may be altered during the course of the study based on newly available data (eg, to obtain data closer to the time of peak or trough matrix concentrations) to ensure appropriate monitoring.

Plasma samples will be used to analyse the PK of AZD8233. Samples collected for analyses of AZD8233 concentration may also be used to evaluate safety or efficacy aspects related to concerns arising during or after the study.

Samples will be collected, labelled, stored, and shipped as detailed in the Laboratory Manual.

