#### **8.5.1.1 Determination of Drug Concentration**

Samples for determination of drug concentration (AZD8233 full lengths ASOs) in plasma will be assayed at bioanalytical test sites operated by or on behalf of AstraZeneca, using an appropriately validated bioanalytical method. Full details of the analytical method used will be described in a separate bioanalytical report.

Placebo samples will not be analysed, unless there is a need to confirm that correct treatment has been given to study participants.

Drug concentration information that would unblind the study will not be reported to investigative sites or blinded personnel until the study has been unblinded.

Incurred sample reproducibility analysis or additional assay development/validation work, if any, will be performed alongside the bioanalysis of the test samples. The results from the evaluation, if performed, will be reported in a separate Bioanalytical Report.

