## **8.5.2 Immunogenicity Assessments**

Blood samples for immunogenicity assessments (ADA) will be collected according to the SoA (Table 1).

The presence or absence of ADAs will be determined in the plasma samples using a validated bioanalytical method. A tiered testing scheme will be employed, with the first step being screening. Samples found positive in the screening step will be tested in the confirmatory step. Samples confirmed positive for ADA in the confirmatory step will undergo endpoint titre determination. Full details of the analytical method and analyses performed will be described in a separate bioanalytical report.

ADA samples may also be further tested for characterisation of the ADA response. Study results may be reported independently to ADA follow-up.

Samples will be collected, labelled, stored, and shipped as detailed in the Laboratory Manual.

Participants with treatment-emerging ADA-positive titres will be asked to return to provide another sample 3 months after the first positive sample to evaluate whether ADAs persist. If the sample taken 3 months later is ADA-positive, the participant will be asked to return to provide a sample in another 3 months. If the sample is ADA-positive at 6 months, the Investigator and the medical monitor will discuss additional actions and decide on future monitoring frequency. Participants with treatment-induced ADAs are considered ADA-positive until levels have returned to baseline or levels have dropped 97% from maximum.

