**Table 2 Populations for Analysis**

Population/Analysis set	Description
All enrolled subjects	All participants who sign the ICF.
All randomized subjects	All participants who were randomized. Participants will be analysed according to the treatment to which they were randomized.
Full analysis set	All randomized participants who received at least one dose of IP, in accordance with the intention to treat principle. Participants will be included in the analysis according to the treatment to which they were randomized. This is the primary analysis set.
Safety analysis set	All participants randomly assigned to study treatment and who take at least 1 dose of study treatment and for whom any post-dose data are available. Participants will be analysed according to the treatment which they actually received. If a participant received study intervention from the wrong kit for only part of the treatment duration and then switched to another, the associated treatment group for that participant will be the treatment group that participant was randomized to.
ADA analysis set	All participants randomly assigned to study treatment and who take at least 1 dose of study treatment and had at least one ADA assessment available. Participants will be included in the analysis according to the treatment to which they were randomized.
PK analysis set	All participants in the full analysis set who have at least one PK sample post dose. A patient will be considered as having at least one PK sample post dose if he has at least one plasma concentration that is not below LLOQ after the first dose. Subjects will be analysed according to the treatment which they actually received. However, only samples taken on patients planned to receive active

	treatment are analysed. Thus, patients planned to receive placebo but who finally received active treatment will not have any result available.
--	---

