All immunogenicity parameters will also be reported in a listing for the full analysis set. Days from previous dose of IP will be calculated as the ADA date minus date of previous dose +1. Days from previous dose of IP for ADA measured during pre-treatment period will be set to missing. Listings of all subjects excluded from the ADA analysis set will also be provided. The listing will be based on all enrolled subjects.

The following figures will be also provided for complete analysis only:

A spaghetti plot figure with individual plotted ADA-titres over time in subjects with any positive ADA-response, one graph per treatment group (including placebo).

A boxplot exploring ADA positive vs ADA negatives impact on PK concentrations over time, percent change on PCSK9 and percent change on LDL over time, one graph per treatment group (including placebo).

A figure showing the percentage of subjects with positive ADA results over time.

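### Protocol 6.3 gives the randomisation list to staff assaying plasma samples without limiting it to PK; as worded it also reaches the ADA assay, which has no documented need for it

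*Protocol*

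**What the plan says.** The access rule closes Protocol section 6.3: "The laboratory vendor personnel performing the bioanalyses of the plasma samples will have access to the randomization list". The section does not define which bioanalyses are meant or what the list is for.

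For PK, Protocol 8.5.1 says "Plasma samples will be used to analyse the PK of AZD8233", and 8.5.1.1 adds "Placebo samples will not be analysed, unless there is a need to confirm that correct treatment has been given to study participants". The PK analysis set in SAP Table 2 follows the same rule: "only samples taken on patients planned to receive active" treatment are assayed.

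For ADA, Protocol 8.5.2 says "The presence or absence of ADAs will be determined in the plasma samples using a validated bioanalytical method". It then sets out screening, confirmation and titre steps and refers to a bioanalytical report. A note to the Schedule of Activities reads "Samples to be obtained from all treatment arms unless specified in the table", and neither the ADA row nor its footnote excludes an arm. SAP 4.2.5.4 plots individual ADA titres over time, "one graph per treatment group (including placebo").

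**The concern.** The sentence sits in the section on minimising bias, and it is an access rule, not a missing detail. A laboratory that followed it literally could release treatment codes to the analysts who call ADA samples positive or negative.

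Development of ADA and titre is a secondary endpoint. It is summarised by treatment group, and ADA status is carried into other displays: adverse events by ADA category, and plots of drug concentration, PCSK9 and LDL by ADA status. If calls are made with treatment known, a difference between arms in ADA incidence is open to a challenge that blinding the analysts would have removed. No offsetting benefit is documented, because only the PK assay has a stated use for the list.

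**Working it through.** No formula applies to the main question, so the check sets the sections side by side.

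**1. What the sentence covers as worded.** Section 6.3 sets two conditions: the work is bioanalysis, and the material is the plasma samples.

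| Assay | Called plasma samples? | Called bioanalytical? | Covered as worded? |
|---|---|---|---|
| PK | Yes (Protocol 8.5.1) | Yes (8.5.1.1) | Yes |
| ADA | Yes (8.5.2) | Yes (8.5.2) | Yes |
| LDL-C, PCSK9 | Endpoints are defined in plasma (Table 3, e.g. "Absolute change from baseline in log-transformed PCSK9 in plasma"), but 8.5.3.1 calls them blood samples | No; Table 7 calls them pharmacodynamic laboratory assessments | Not established |

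The blood-sample label alone does not separate the rows, since 8.5.2 also opens by referring to blood samples before it speaks of plasma samples. Nor does the SAP's phrase central laboratory: it is used for LDL-C and PCSK9 (3.3.1.1, 3.3.2.1) and, with the word external added, for PK (3.3.2.5). What separates them is that the protocol applies the term bioanalytical to PK and ADA and never to LDL-C or PCSK9.

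**2. Who needs the list.** PK does, because samples are selected for assay by planned treatment. For ADA, collection in every arm does not settle the matter, since PK samples are also drawn in every arm and the placebo ones are left unassayed. What settles it is the reporting. The ADA analysis set in SAP Table 2 takes randomised, dosed participants with an ADA assessment and excludes no arm, and the titre plots include placebo. ADA samples from all arms must therefore be assayed, and no selection by arm arises.

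**3. Whether another passage limits access.** The code-breaking rules in Protocol 6.3 deal with emergencies, certain serious adverse events and the planned analyses. The firewall in 8.5.1.1 keeps unblinding drug concentrations from sites and blinded personnel. SAP 1.1 assigns the primary analysis to an independent unblinded team. None of these restricts the laboratory's list to PK staff or says that ADA analysts stay blinded.

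**4. How a call reaches the endpoint.** SAP 4.2.5.4 builds prevalence, incidence and persistent or transient positivity from sample results, and counts a missing result as negative when deriving these categories. Whether a result is reported can therefore change a participant's category. As a scale only: 108 / 4 = 27 participants per arm, so one changed category moves an arm's percentage by 1/27 = 3.7 points. With 80 / 4 = 20 per arm it is 1/20 = 5.0 points. This shows how sensitive the endpoint is to one participant; it does not estimate bias.

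**The case against.** The strongest reply is that section 6.3 means PK only. Elsewhere the protocol uses the noun bioanalysis only in the drug-concentration section. Section 8.5.1 speaks of plasma samples for PK, the schedule has a row for PK plasma samples, and the rule on placebo samples supplies the motive. That reading is plausible, but it is not written down, and the wording of 8.5.2 fits the access sentence just as well.

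Second, ADA testing follows a fixed sequence with a validated method, and the analytical details lie in a bioanalytical report and laboratory manual that are not available here. This stands as a reason to expect a small effect. A reader might infer that analysts would choose to re-run unexpected ADA or PCSK9 values according to arm. The documents describe no such discretion and give no re-assay rule either way, so the point does not rest on it.

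Third, the synopsis declares only participant and Investigator blinding, and nothing shows the list reaching sites or blinded sponsor staff. This also stands: the fault is unclear scope, not a contradiction.

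A reader might also infer from the plasma endpoints in Table 3 that the primary LDL-C endpoint and PCSK9 are assayed unblinded. The documents do not support that. The word plasma names the matrix, and neither document calls those assays bioanalysis. They do not exclude it either, which is why a clarifying clause is worth adding.

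**Conclusion.** The point holds for ADA. As worded, Protocol 6.3 lets analysts of a secondary endpoint know treatment, while only the PK assay has a documented need for the list. That ADA has no need of it is an inference from its reporting in every arm; the documents do not say so directly.

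The bias risk is avoidable and probably small, and it cannot be quantified from the documents. Sample size, power and alpha are unaffected. No effect on the primary endpoint is shown, because coverage of LDL-C and PCSK9 remains unresolved. The conclusion assumes that the laboratory manual and vendor agreements do not already restrict access. If they do, the change merely brings the protocol into line with practice.

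**What to change.** Reword the last sentence of Protocol 6.3 so that only personnel performing the AZD8233 concentration assay receive the list, solely to select samples. Add that personnel assaying ADA, and for clarity LDL-C, PCSK9 and other lipids, have no access to treatment codes until the study is unblinded. Define that moment as after final database lock: the SAP's primary analysis follows Visit 10 (Week 12), when ADA samples at Weeks 16, 20 and 24 may still be outstanding.

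If the same vendor staff run both assays, separate the access or complete the ADA calls before the list is used. The documents do not say how the vendor is staffed, so any scheduling effect cannot be sized.

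The cost is a sentence or two in the protocol, mirrored in the laboratory manual. PK loses nothing and no analysis changes. Under Appendix A 1, protocol amendments go to ethics committees and, where applicable, regulators, so the wording is best carried with the next amendment. The laboratory instruction can be tightened in the meantime.

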## **6.4 Study Intervention Compliance**

When participants are dosed at the site, they will receive study intervention directly from the Investigator or designee, under medical supervision. The date, and time if applicable, of dose administered in the clinic, as well as the anatomical location of the injection site, will be recorded in the source documents and recorded in the eCRF. The dose of study intervention and study participant identification will be confirmed at the time of dosing by a member of the

study site staff other than the person administering the study intervention.

Dosing visits may be undertaken as home visits by site staff. If participants are dosed at home, they will receive study intervention directly from site staff. The dose administered at home will be recorded in the source documents.

## 6.5 Concomitant Therapy

Any medication (including over-the-counter or prescription medicines, vitamins, and/or herbal supplements) or vaccine that the participant is receiving at the time of enrolment or receives during the study must be recorded along with:

- Reason for use
- Dates of administration including start and end dates
- Dosage information including dose and frequency

Investigators may prescribe concomitant medications or treatments deemed necessary to provide adequate care for participants except for those medications excluded below or listed in the exclusion criteria. Specifically, participants should receive full supportive care during the study as deemed appropriate, and in accordance with local guidelines.

The following medical restrictions apply:

- Medications / therapies specified in the exclusion criteria are prohibited from use for the duration of the participant's involvement in the study.
- All study participants should be receiving moderate-or high-intensity statin therapy as defined by the ACC/AHA guidelines on blood cholesterol management, or according to local guidelines.
- Participants should be on stable medication for  $\geq 3$  months prior to screening with no planned medication or dose change during study participation. The exception to this restriction is for fenofibrate; if the participant is receiving fenofibrate, the therapy must be stable for at least 6 weeks prior to randomization at a dose that is appropriate for the duration of the study in the judgement of the Investigator. Other fibrate therapy (and derivatives) are prohibited.
- Participants should not be on any anti-platelet therapy other than low-dose aspirin ( $\leq 100$  mg/day).
- Participants must abstain from making dose changes and taking new prescription or non-prescription drugs without consultation of the Investigator (including vitamins and dietary or herbal supplements) within 7 days (or 14 days if the drug is a potential enzyme inducer) or 5 half-lives (whichever is longer) before the start of study intervention (Visit 3) until completion of the follow-up visits.

- Paracetamol/acetaminophen, at doses of  $\leq 2$  g/day, is permitted for use any time during the study. Other concomitant medication may be considered on a case-by-case basis by the Investigator in consultation with the Medical Monitor if required.
- The Medical Monitor should be contacted if there are any questions regarding concomitant or prior therapy.

### **6.5.1 Rescue Medicine**

The study will not supply any specific rescue medication. Please see Section 6.5 on concomitant therapy for additional instructions.

The date and time of any rescue medication administration or respective dose change must be recorded including:

- Name of medication;
- Reason for use / change;
- Dates of administration including start and end dates;
- And dosage information including dose and frequency.

### **6.6 Dose Modification**

No dose modification is planned.

### **6.7 Intervention after the End of the Study**

There is no planned intervention following the end of the study.

## **7. DISCONTINUATION OF STUDY INTERVENTION AND PARTICIPANT DISCONTINUATION/WITHDRAWAL**

### **7.1 Discontinuation of Study Intervention**

An **individual participant** will not receive further study treatment if any of the following occur in the participant in question:

- Confirmed platelet count  $< 75,000/\mu\text{L}$  (see [Appendix F](#) in case of uninterpretable platelet count)
- Hy's Law defined as 'an increase in AST or ALT  $\geq 3 \times \text{ULN}$  and TBL  $\geq 2 \times \text{ULN}$ ', where no other reason, other than the study treatment, can be found to explain the combination of increases
- ALT or AST  $> 8 \times \text{ULN}$
- ALT or AST  $> 5 \times \text{ULN}$  for  $> 2$  weeks
- ALT or AST  $> 3 \times \text{ULN}$  and TBL  $> 2 \times \text{ULN}$  or INR  $> 1.5$

- ALT or AST > 3 × ULN with the appearance of fatigue, nausea, vomiting, right upper quadrant pain or tenderness, fever, rash, and/or eosinophilia (> 5 %)
- Confirmed increase in serum creatinine of 0.3 mg/dL from baseline
- Confirmed 25% decline in eGFR from baseline
- Confirmed new-onset haematuria, albuminuria (UACR ≥ 300 mg/g), or proteinuria (UPCR ≥ 500 mg/g)
- Hypersensitivity reaction CTCAE grade 3 or higher

Participants may be discontinued from study intervention in the following situations:

- Participant decision. The participant is at any time free to discontinue treatment, without prejudice to further treatment
- Adverse Event
- Severe non-compliance with the CSP

If a participant discontinues study treatment, he or she will be encouraged to return to the study site for the EDV (see Table 1). Where possible, the EDV should be at the next visit according to the original visit schedule, unless consent is withdrawn from further study participation. To secure recommended safety follow-up, participants attending an EDV should also be asked to continue to return for their originally scheduled visits for a total of three months, unless they are unable to or unwilling to return. Note that discontinuation from study intervention is NOT the same thing as a withdrawal from the study.

See the SoA for data to be collected at the time of intervention discontinuation and follow-up and for any further evaluations that need to be completed.

